6.4 Accountability

Subjects will return all study bottles and unused study drug at each clinic visit for drug accountability to be performed. The Investigator or their appointed designee is responsible for ensuring that deliveries of study drug are correctly dispensed and recorded, that the product is handled and stored safely and properly, and that it is only being given to subjects in accordance with this protocol.

Sites will keep a current log of drug accountability recording:

- Temperature logs for on-site storage refrigerator.
- What drug supply was received from the Sponsor.
- What drug supply was dispensed to each subject.
- What drug supply is current in inventory.
- What drug supply was destroyed or returned to the Sponsor for destruction.

Note: Drug accountability is the responsibility of the Investigator; a written account will be required for all discrepancies.

The Sponsor's designated Monitor must verify all accountability records during periodic monitoring visits. Unused and used study drug must be stored on site until such accountability has taken place and authorization is received from the Sponsor or Sponsor's designee that the study drug may be returned or destroyed.

6.5 Overdose/Toxicity Management

No specific pharmacologic antagonist or antidote exists for CT1812. Therefore, overdose or clinical toxicity should be managed with supportive care and pharmacologic treatments directed at specific symptoms (i.e., benzodiazepines for agitation or antipyretics for fever).

6.6 Blinding, Randomization and Matching Subjects

This is a double-blind, placebo-controlled study. Study drug will consist of CT1812 and a matching placebo. The placebo will be identical in appearance to the active CT1812.

The non-blinded statistician assigned to the trial will generate a list with the appropriate number of multiple digit individual study IDs for each arm, randomly assigned to either active or placebo treatment.

7 INVESTIGATORS, SITES AND DURATION

7.1 Investigator and Site

This is a multi-center trial and will include up to approximately 30 qualified investigator sites.

7.2 Duration of Study

Screening procedures will occur on Days -42 to -1. Eligible subjects will return to the clinic at Baseline/Day 1 visit for randomization into the trial. Daily dosing will continue through Day 182. The maximum total duration of subject participation in the study is up to 254 days including screening.

7.3 Use of Remote Measures in Extenuating Circumstances

Study visits should be performed in the clinic as specified in Section 9 and Table 1 if possible. However, under extenuating circumstances, after consultation with and approval by the medical monitor, specific alternative measures may be implemented (e.g., if a subject is unable to travel to the study site due to safety concerns and/or local restrictions related to COVID-19 or other emerging events) in order to ensure the safety of subjects, site investigators, and site personnel while maintaining compliance with GCP and minimizing impact to the integrity of the study. The Screening Visit, Day 1 (Baseline), Days 28, 56, 70, 154 and 182 must be performed in the clinic. The following remote measures may be implemented. Additional details can be found in the Study Reference Manual.

- Consent or reconsent may be obtained remotely in writing (or verbally, with follow-up written confirmation), as allowed by local regulations.
- Study drug may be shipped directly from the site to the subject, as applicable and as allowed by local regulations.
- Study visits (except for those noted above) may be conducted as in-home visits by qualified personnel.
- Study assessments to evaluate safety may be performed or overseen by qualified personnel conducting the in-home visits.

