4.2 Secondary Objectives

- To assess exploratory measures of efficacy at baseline, 3 months, and 6 months.
- To assess pharmacodynamic target engagement and potential biomarker evidence of disease modification.

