- Dispense study drug supply and instructions for at home dosing
- Instruct subject to return for Day 42 visit including instructions to bring study drug with them to the Day 42 visit

9.2.5 Visit 5 Subject Day 42

The subject will return to the clinic for the following assessments:

- Measure and record vital signs
- Draw blood and prepare sample for serum chemistry and Blood should be drawn within an hour of urine collection.
- Collect urine samples for urinalysis
- Record any AEs.
- Record changes in medications.
- Conduct drug accountability, return study drug to the subject for continued dosing
- Instruct subject to return for Day 56 visit including instructions to hold dose on morning of Day 56 visit and to bring study drug with them

9.2.6 Visit 6 Study Day 56

The subject will return to the clinic.

Pre-dose Assessments:

- Administer C-SSRS Since Last Visit version
- Perform brief physical examination
- Measure and record vital signs
- Draw blood and prepare sample for serum chemistry and hematology Blood should be drawn within an hour of urine collection.
- Collect blood samples for PK
- Collect urine samples for urinalysis
- Record any AEs.
- Record changes in medications.
- Conduct drug accountability
- Administer Day 56 dose with food.

Post-dose Assessments:

- Dispense study drug supply and instructions for at home dosing
- Instruct subject to return for Day 70 visit including instructions to bring study drug with them to the Day 70 visit

9.2.7 Visit 7 Study Day 70

The subject will return to the clinic for the following assessments:

- Measure and record vital signs
- Draw blood and prepare sample for serum chemistry and hematology Blood should be drawn within an hour of urine collection.

- Collect urine samples for urinalysis
- Record any AEs.
- Record changes in medications.
- Conduct drug accountability, return study drug to the subject for continued dosing
- Instruct subject to return for Day 98 visit including instructions to hold dose on morning of Day 98 visit and to bring study drug with them

9.2.8 Visit 8 Study Day 98

The subject will return to the clinic.

Pre-dose Assessments:

- Administer MOCA, CDR, ADCS-ADL, NPI, ADCS-CGIC, MDS-UPDRS Part III, CAF and ESS
- Administer C-SSRS Since Last Visit version
- Perform brief physical examination
- Measure and record vital signs
- Draw blood and prepare sample for serum chemistry and hematology. Blood should be drawn within an hour of urine collection.

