10 SAMPLE COLLECTION

10.1 Blood Sampling for PK and Exploratory Plasma Biomarkers

Blood samples for the measurement of plasma CT1812 levels and exploratory plasma biomarkers will be drawn at the following times during the study:

- Day 1 (baseline) whole blood sample collection for Future Biomedical Research (FBR) (pharmacogenomics) including potential genetic analyses (see section 10.2). Within 1.25 hours prior to dosing
- PK: Days: 1, 28, 56, 98, 154, and 182: within 1.25 hours prior to dosing.
- PD plasma biomarkers: Screening and Days: 1, 28, 98, and 182: within 1.25 hours prior to dosing
 - Note: If the PD sample cannot be collected prior to dosing on Day 1 baseline, the subject may not receive the first dose of study drug. Dosing will be delayed until this successful collection of this pre-dose baseline sample.

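### The in-clinic visit list names Day 70, which has no efficacy assessment, and omits Day 98, the Month 3 efficacy visit, so some Month 3 scores may be missing or obtained outside the clinic

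*Protocol*

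**What the plan says.** Protocol section 7.3 makes clinic visits the default. It adds that "under extenuating circumstances, after consultation with and approval by the medical monitor, specific alternative measures may be implemented". It then fixes the visits to which this does not extend: "The Screening Visit, Day 1 (Baseline), Days 28, 56, 70, 154 and 182 must be performed in the clinic". For the rest, "Study visits (except for those noted above) may be conducted as in-home visits by qualified personnel". On what may be done at home, it says: "Study assessments to evaluate safety may be performed or overseen by qualified personnel conducting the in-home visits". It names no efficacy scale, PK sample or biomarker sample, and refers to a Study Reference Manual for further detail.

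Section 9.2.8 gives Day 98 the same instruction as baseline: "Administer MOCA, CDR, ADCS-ADL, NPI, ADCS-CGIC, MDS-UPDRS Part III, CAF and ESS". Section 9.2.7 has nothing of the kind for Day 70. Section 10.1 sets the biomarker draws: "PD plasma biomarkers: Screening and Days: 1, 28, 98, and 182: within 1.25 hours prior to dosing".

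A secondary objective (section 4.2) is "To assess exploratory measures of efficacy at baseline, 3 months, and 6 months". SAP section 11.1 uses Day 28, Month 3 and Month 6 as the three MMRM responses. SAP section 10.4 imputes nothing, and only lists early-termination data from before Day 170. SAP section 10.7 makes MoCA change at 6 months the key efficacy endpoint.

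**The concern.** The visits that must be in clinic should include those whose data are hardest to collect elsewhere. Section 7.3 instead secures a visit that holds only safety procedures and drug accountability, and leaves open the visit that holds the Month 3 efficacy battery. Several of those measures depend on setting. The CDR is a laptop battery to be given at a repeatable time of day (sections 9.2.1 and 11.1.4). The motor scale is a physical examination. The CGIC is rated by an independent rater where the site has one (section 11.1.10).

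At stake are a time point named in a secondary objective and one of three post-baseline MMRM responses. For a subject who stops treatment between Day 98 and Day 170, Day 98 is also the last scheduled efficacy value that is summarised; without it only Day 28 remains. Plasma biomarkers followed over time are analysed after baseline only at Day 98 and end of study (SAP section 13.1).

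**Working it through.** **1. Compare the list with the schedule** (sections 7.3, 9.2 and 10.1; Table 1).

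| Visit | Must be in clinic | Efficacy battery | In-clinic dose and PK | Plasma biomarker | C-SSRS | ECG |
|---|---|---|---|---|---|---|
| Day 1 | yes | yes | yes | yes | yes | yes |
| Day 28 | yes | yes | yes | yes | yes | yes |
| Day 56 | yes | no | yes | no | yes | no |
| Day 70 | **yes** | no | no | no | no | no |
| Day 98 | **no** | yes | yes | yes | yes | yes |
| Day 154 | yes | no | yes | no | yes | no |
| Day 182 | yes | yes | yes | yes | yes | yes |

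- Efficacy days {1, 28, 98, 182} minus the list leaves {98}.
- In-clinic dosing and PK days {1, 28, 56, 98, 154, 182} minus the list leaves {98}.
- The list after Screening minus the dosing and PK days leaves {70}.

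The unlisted visits are Days 14, 42, 98, 126 and 210. In Table 1, Day 70 has the same content as Days 14, 42 and 126, none of which is listed. Day 98 is the only unlisted visit with more than safety and accountability procedures.

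**2. Is Day 98 Month 3?** The documents never say so outright. At 30.4375 days per month, 98/30.4375 = 3.2 and 70/30.4375 = 2.3. No other efficacy visit lies between Day 28 and Day 182.

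**3. Number of records.** No remote-visit rate is given. Assume 5-10% of Day 98 visits are at home: 0.05 × 120 = 6 and 0.10 × 120 = 12. This is an upper figure, because it allows for no dropout before Day 98.

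**4. Reach into Month 6.** Day 182 is on the list. A missing Month 3 value bears on the Month 6 MMRM estimate mainly through subjects who later drop out. The plan allows 120 − 105 = 15 dropouts. If all came after Day 98, and remote visits were independent of dropout, 15 × 0.05 = 0.75 to 15 × 0.10 = 1.5 subjects would be affected, so about 1 to 2.

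**5. Illustration at Month 3.** The plan's own figure reproduces. For a two-sided t-test at 0.05 with 70 versus 35 subjects, the noncentrality is 0.78 / (1.32 × √(1/35 + 1/70)) = 2.85. Power is 80.7%, and 105 is the smallest total reaching 80% under 2:1 allocation. Suppose the same difference and SD held at Month 3, with no borrowing across visits, and a share f of scores were missing. The standard error would grow by 1/√(1 − f):

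| f | Subjects left | SE ratio | Power |
|---|---|---|---|
| 0% | 105 | 1.000 | 80.7% |
| 5% | 99.75 | 1.026 | 78.7% |
| 10% | 94.5 | 1.054 | 76.4% |
| 20% | 84 | 1.118 | 71.3% |

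The trial was not sized for Month 3. These figures give scale only, and treat every home visit as a missing score.

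**The case against.** The exposure is narrow. Remote visits need extenuating circumstances and the medical monitor's approval, and section 9.2.8 itself has the subject return to the clinic. All of that stands, and it limits the size.

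A reader might infer that each in-home Day 98 visit loses everything scheduled that day. The documents do not support this. The ECG is a safety measure, so section 7.3 allows it at home. Efficacy scales and biomarker draws are not expressly barred; blood for safety tests is due that day anyway, and the NPI, CAF and ADCS-ADL are informant-based. The Study Reference Manual, not available here, may cover remote testing. The supported wording is that data may be missing or taken in a different setting.

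It can also be said that efficacy is not the list's criterion, since Days 56 and 154 have no battery, and that Day 70 closes the two-weekly phase, so the choice may be deliberate. That cannot be excluded. But Days 56 and 154 are dosing and PK days and Day 70 is not, and no section gives a reason for preferring it to Day 98.

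Finally, requiring a clinic visit does not bring in a subject who cannot travel. With a ±2-day window, the visit could be missed and its safety data put at risk. This stands, and the fix must allow for it. The SAP does count missed assessments as possible major deviations (section 9.2) and lists COVID-19 impact (section 15.8), but neither identifies efficacy scores obtained outside the clinic.

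**Conclusion.** The inconsistency is real: section 7.3 does not fit Table 1 or sections 9.2.7, 9.2.8 and 10.1, and no other section repairs it. A substitution of 70 for 98 is the likeliest explanation, though not a proven one. Followed as written, the rule leaves the Month 3 efficacy visit as the only efficacy visit that can move to the home, without saying how its scales are to be handled.

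The size is modest: at most 6-12 of 120 Month 3 records on an assumed 5-10% remote rate. The day's biomarker sample, one of two post-baseline values analysed, is also exposed. A reader might infer that the key endpoint is threatened. It is not: Month 6 MoCA falls on Day 182, which is on the list, and on the assumptions above the indirect effect through later dropouts concerns about 1 to 2 subjects. The correction is worth making because a named secondary time point is exposed and the remedy is cheap.

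**What to change.** - **Protocol section 7.3:** reconcile it with Table 1 and sections 9.2.7, 9.2.8 and 10.1. Add Day 98 to the in-clinic list and check whether Day 70 was meant.
- **Subjects who cannot travel for Day 98:** state which efficacy scales, if any, may be collected and whether the biomarker sample may be drawn, so that safety data are still obtained. Align the Study Reference Manual.
- **SAP:** before unblinding, flag Day 98 efficacy scores obtained outside the clinic and repeat the MoCA MMRM without them. This remains useful if Day 98 visits are already complete and a protocol change would come too late.

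The cost is a short clarification to the protocol and manual, a flag in the data and one extra model run. The downside is that a few Day 98 visits may be delayed, fall outside the 2-day window or be missed; the second item limits this.

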7.4 Termination of Study

This study may be terminated at the discretion of the Sponsor.

8 STUDY POPULATION

8.1 Number of Subjects

Approximately 120 subjects will be randomized.

8.2 Inclusion Criteria

Subjects may be included in the study only if they meet all of the following criteria:

- 1) Subjects or their Legally Authorized Representative (LAR) (or designee as applicable by local law) must provide written informed consent to the study procedures prior to any study procedures.
- 2) Subjects must have a caregiver/ study partner who in the opinion of the site principal investigator, has contact with the study subject for a sufficient number of hours per week to provide informative responses on the protocol assessments, oversee the administration of study drug, and is willing and able to participate in all clinic visits and some study assessments. The caregiver/ study partner must provide written informed consent to participate in the study.
- 3) Men or women 50-85 years of age (inclusive), meeting criteria for probable DLB (as defined by the 4th report of the DLB Consortium, McKeith et al., 2017).
- 4) Men willing to comply with acceptable form of contraception or women of non-childbearing potential as defined below:

- i) Non-childbearing potential for women is defined as postmenopausal (last natural menses greater than 24 months) or undergone a documented bilateral tubal ligation or hysterectomy. If last natural menses less than 24 months, a serum FSH value confirming post-menopausal status can be employed.
 - ii) Male subjects who are sexually active with a woman of childbearing potential must agree to use condoms during the trial and for 3 months after last dose unless the woman is using an acceptable means of birth control. Acceptable forms of birth control include abstinence, birth control pills, or any double combination of: intrauterine device (IUD), male or female condom, diaphragm, sponge, and cervical cap.
- 5) MRI (or CT scan due to contraindication of MRI, if approved by medical monitor) obtained during screening consistent with the clinical diagnosis of DLB and without findings of significant exclusionary abnormalities. An historical MRI (or CT scan), up to 1 year prior to screening, may be used as long as there is no history of intervening neurologic disease or clinical events (such as a stroke, head trauma etc.) and the subject is without clinical symptoms or signs suggestive of such intervening events.
 - 6) MMSE 18-27 inclusive.
 - 7) If receiving acetylcholinesterase inhibitors (AChEI), memantine or a combination of the two, must have been on a stable dose for at least 12 weeks before the screening visit, with no plans for dose adjustment during the study. Treatment-naïve subjects can be entered into the study, but there should be no plans to initiate treatment with AChEIs or memantine from Screening to the end of the study.
 - 8) Stable pharmacological treatment of any other chronic conditions for at least 30 days prior to screening.
 - 9) Formal education of eight or more years.
 - 10) Subjects living at home or in an assisted living facility.
 - 11) Ability to swallow capsules.
 - 12) Must consent to apolipoprotein E (ApoE) genotyping.
 - 13) Subjects shall be generally healthy with mobility (ambulatory or ambulatory-aided, i.e., walker or cane), vision and hearing (hearing aid permissible) sufficient for compliance with testing procedures.
 - 14) Must be able to complete all screening evaluations.

8.3 Exclusion Criteria

Subjects will be excluded from the study if any of the following conditions apply:

- 1) Any neurological condition that may be contributing to cognitive impairment above and beyond those caused by the subject's DLB, including any co-morbidities detected by clinical assessment or MRI (or CT scan due to contraindication of MRI, if approved by medical monitor).
- 2) History of transient ischemic attacks or stroke within 12 months of screening.
- 3) Parkinsonian (extrapyramidal) features with Modified Hoehn and Yahr stage 4 or higher or any diagnosis of Parkinson's disease or parkinsonism that preceded cognitive decline by more than one year.
- 4) Hospitalization (except for planned procedures) or change of chronic concomitant medication within one month prior to screening.
- 5) Any major psychiatric diagnosis, including schizophrenia, bipolar disorder, and current major depressive disorder as per Diagnostic and Statistical Manual of Mental Disorders Fifth Edition.
- 6) Geriatric Depression Scale score ≥ 6 . (Subjects with a GDS >6 may be allowable if the investigator does not believe the subject is clinically depressed. Investigators should contact the medical monitor to discuss eligibility.)
- 7) Subjects living in a continuous care nursing facility.
- 8) Contraindication to the MRI examination for any reason or, in lieu of an MRI, if the subject is unwilling or unable to undergo a CT scan, or if the CT scan is not approved by the medical monitor. (Note: CT scan may be substituted for an MRI if subjects are unable to tolerate an MRI or an MRI is contraindicated for medical reasons, if the proposed CT scan is discussed and approved by the medical monitor on a case-by-case basis).
- 9) Screening MRI (or CT scan due to contraindication of MRI if approved by medical monitor) or historical MRI/CT scan, if applicable, of the brain indicative of significant abnormality, including, but not limited to, prior hemorrhage or infarct $> 1 \text{ cm}^3$, >3 lacunar infarcts, cerebral contusion, encephalomalacia, aneurysm, vascular malformation, subdural hematoma, hydrocephalus, space-occupying lesion (e.g. abscess or brain tumor such as meningioma). If a small incidental meningioma is observed, the medical monitor may be contacted to discuss eligibility.
- 10) Clinical, laboratory findings or medical history consistent with:

- a) Other primary degenerative dementia, (frontotemporal dementia, Huntington's disease, Creutzfeldt-Jakob Disease, Down syndrome, etc.).
 - b) Other neurodegenerative condition (amyotrophic lateral sclerosis, etc.).
 - c) Seizure disorder.
 - d) Other infectious, metabolic or systemic diseases affecting the central nervous system (syphilis, present hypothyroidism, present vitamin B12 or folate deficiency, other laboratory values etc.).
- 11) Clinically significant, advanced or unstable disease that may interfere with outcome evaluations, such as:
- a) Chronic liver disease, liver function test abnormalities or other signs of hepatic insufficiency (ALT, AST, alkaline phosphatase > 1.5 ULN, lactate dehydrogenase (LDH) > 1.5 x ULN).
 - b) Respiratory insufficiency which requires the use of supplemental oxygen.
 - c) Renal insufficiency eGFR < 50 mL/min based on the CKD-EPI formula.
 - d) Heart disease (myocardial infarction, unstable angina, heart failure, cardiomyopathy within six months before screening).
 - e) Bradycardia (<50 beats/min.) or tachycardia (>100beats/min.). If heart rate is below 50 beats/min or above 100 beats/min, the heart rate assessment may be repeated to assess eligibility.
 - f) Poorly managed hypertension (systolic >160 mm Hg and/or diastolic >95 mm Hg) or hypotension (systolic <90 mm Hg and/or diastolic <60 mm Hg).
 - g) Uncontrolled diabetes defined by HbA_{1c} >7.5% in subjects with diabetes, Only those subjects with known diabetes are required to get a HbA_{1c} at screen.
- 12) History of cancer within 3 years of screening with the exception of fully excised non-melanoma skin cancers or non-metastatic prostate cancer that has been stable for at least 6 months.
- 13) Seropositive for human immunodeficiency virus (HIV).
- 14) History of acute/chronic hepatitis B or C and/or carriers of hepatitis B (seropositive for hepatitis B surface antigen [HbsAg] or anti-hepatitis C [HCV] antibody).
- 15) Clinically significant abnormalities in screening laboratory tests, including:

- a) Hematocrit less than 35% for males and less than 32% for females, absolute neutrophil cell count of 1500/uL (with the exception of a documented history of a chronic benign neutropenia, absolute lymphocyte count <900/ uL), or platelet cell count of < 120,000/uL; INR >1.4 or other coagulopathy, confirmed by repeat assessment of:
 - i) Hematocrit
 - ii) Neutrophil count
 - iii) Lymphocyte count
 - iv) Platelet count
- 16) Disability that may prevent the subject from completing all study requirements (e.g. blindness, deafness, severe language difficulty, etc.).
- 17) Within 4 weeks of screening visit or during the course of the study, concurrent treatment with antipsychotic agents, antiepileptics, centrally active anti-hypertensive drugs (e.g., clonidine, l-methyl dopa, guanidine, guanfacine, etc.), sedatives, opioids, mood stabilizers (e.g., valproate, lithium); or benzodiazepines, with the following exceptions:
 - a) At the discretion of the investigator, lorazepam or another anxiolytic may be administered as per local standard of care prior to MRI scan or optional lumbar puncture. Note neurocognitive testing should not be done within 24 hours of administration of conscious sedation..
 - b) Stable use of clonazepam for at least 30 days as indicated for REM Sleep Behavioral Disorder (RBD)
 - c) Stable use of atypical antipsychotics (e.g., quetiapine, pimavanserin) for at least 30 days as indicated for delusions and hallucinations secondary to DLB.
- 18) Any disorder that could interfere with the absorption, distribution, metabolism or excretion of drugs (e.g., small bowel disease, Crohn's disease, celiac disease, or liver disease).
- 19) Nootropic drugs except stable doses of acetylcholinesterase inhibitors or memantine.
- 20) Suspected or known drug or alcohol abuse, i.e., more than approximately 60 g alcohol (approximately 1 liter of beer or 0.5 liter of wine) per day indicated by elevated MCV significantly above normal value at screening.
- 21) Suspected or known allergy to any components of the study treatments.
- 22) Enrollment in another investigational study or intake of investigational drug within the previous 30 days or five half-lives of the investigational drug, whichever is longer.

- 23) Intake of drugs or substances potentially involved in clinically significant induction or inhibition of CYP3A4 or P-gp mediated drug interactions with CT1812, within 4 weeks or five half-lives of the interacting drug prior to administration of CT1812 and throughout the course of the study. Grapefruit juice should be avoided in the two weeks prior to dosing and throughout the course of the study. See Appendix A for a complete list of prohibited substances. See Section 9.3.1 for handling of Paxlovid™ administration for COVID infection during the course of study.
- 24) Any prior exposure to immunomodulators, anti Aβ vaccines, passive anti Aβ immunotherapies (e.g., monoclonal antibodies) and/or exposure to BACE inhibitors within the past 30 days.
- 25) Any condition, which in the opinion of the investigator or the sponsor makes the subject unsuitable for inclusion.
- 26) Any vaccination within one week of the baseline visit.

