9.2 Visit Specific Procedures

9.2.1 Visit 1 / Screening

The Screening visit must be performed within 42 days prior to Day 1 – Baseline. The following procedures will be performed at the Screening visit:

- Subjects or their Legally Authorized Representative (LAR) (or designee as applicable by local law) must provide written informed consent to the study procedures prior to any study procedures. The caregiver must also provide written informed consent at this time.
- Evaluate subject eligibility against study inclusion/exclusion criteria.
- Confirm DLB diagnosis (see section Appendix B).
- Record demographic information, confirm ethnicity, alcohol and drug history, educational history and obtain medical history.
- Administer the Mini-Mental State Exam (MMSE) and Geriatric Depression Scale (GDS)
- Administer Modified Hoehn and Yahr
- Administer CAF and ESS
- Administer C-SSRS Screening/Baseline version
- Perform complete physical examination with neurological examination
- Measure and record vital signs
- Perform 12-lead ECG
- MRI (or CT scan due to contraindication of MRI, if approved by medical monitor), unless an historical MRI/CT scan is used.
- Draw blood and prepare samples for APOE status. Apolipoprotein E (ApoE) genotype is associated with the risk and age of onset of DLB. Blood samples (approximately 10 mL) to perform this testing will be collected and will be utilized to further understanding of response to CT1812. The genotyping is mandatory for participation in the study and the results will not be revealed to either the investigator or subject and caregiver.
- Draw blood and prepare samples for coagulation testing (PT/INR), serum chemistry, hematology, viral serology, TSH, FSH (in women who had their last natural menses less than 24 months prior to screening and who are not surgically sterile) and HbA1c (in known

diabetics), Blood should be drawn within an hour of urine collection. Abnormal results at screening will exclude a subject unless the investigator is aware of a specific reason that can explain the abnormality (e.g., elevated CPK 24 hours after strenuous exercise). Should an abnormal lab remain abnormal on repeat the subject will be excluded. Collect blood sample for exploratory biomarker samples

- Collect blood samples for exploratory plasma biomarker analysis
- Collect urine sample for β -HCG pregnancy test for women who are not postmenopausal (last natural menses was less than 24 months ago) that are not surgically sterile.

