12.1.4 Clinical Laboratory Tests

Hematology testing will include red blood cell count, erythrocyte mean corpuscular hemoglobin concentration (MCHC), erythrocyte mean corpuscular volume (MCV), hematocrit, hemoglobin, leukocyte count, and absolute counts of monocytes, neutrophils, basophils, eosinophils and platelets. Coagulation testing (prothrombin time [PT/INR]) will be performed at screening and Day 154 only.

Serum chemistry analyses will include glucose, calcium, albumin, total protein, sodium, potassium, bicarbonate, chloride, magnesium, blood urea nitrogen (BUN), creatinine, creatine kinase, alkaline phosphatase, ALT, AST, bilirubin, lipase, lactate dehydrogenase (LDH) and phosphorus.

In instances where either the AST or ALT are 2x the ULN these tests will be repeated and documented as an unscheduled visit.

Blood draws should occur within 1 hour of urine collection.

Urinalysis will include osmolality, creatinine, calcium, sodium, turbidity, color, specific gravity, pH, protein, glucose, ketones, bilirubin, blood, urobilinogen, nitrite, leukocytes, and microscopic particles. Urine should not be first morning void. Microscopic examination will be performed if urinalysis results are abnormal for bacteria, casts, epithelial cells, erythrocytes, or leukocytes. Urine should be collected within one hour of blood draws for hematology and chemistry panels. It should not be first morning void. Trace protein will be considered positive.

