16.1.3 Protocol Waivers

Protocol waivers will not be granted by the Sponsor in this study.

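### Exclusion 15a gives the neutrophil limit no '<' and prints the lymphocyte limit inside the neutropenia exception, in both copies (wording error, minor)

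*Protocol*

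**What the plan says.** Exclusion 15 in Protocol section 8.3 excludes clinically significant screening laboratory abnormalities and gives item (a) as what that includes. Item (a) runs through hematocrit, neutrophils, lymphocytes, platelets and INR in one sentence. The middle of it reads "absolute neutrophil cell count of 1500/uL (with the exception of a documented history of a chronic benign neutropenia, absolute lymphocyte count <900/ uL", followed by the closing bracket. The next limit in the same sentence is "platelet cell count of < 120,000/uL". It ends "INR >1.4 or other coagulopathy, confirmed by repeat assessment of", followed by four tests, the third being "iii) Lymphocyte count". The synopsis carries the same wording.

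Section 9.2.1 adds a general screening rule. An abnormal result excludes unless the investigator knows of a specific explanation, and "Should an abnormal lab remain abnormal on repeat the subject will be excluded". It also has the site send a subject eligibility form, kept in the study manual, to the medical monitor. Exclusion 25 lets the investigator or sponsor exclude a subject they consider unsuitable.

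**The concern.** These are operative entry limits in a trial whose primary objective is safety, and section 7.1 foresees up to about 30 sites applying them. The sentence does not say which side of 1500/uL excludes, and it prints a low lymphocyte count as part of an exemption. A site following the words and a site following the evident intent could treat the same subject differently under 15a.

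The lymphocyte limit is not a formality for this drug. Section 3.3 names transient lymphocytopenia among the events seen more often at 560 mg in the 28-day Alzheimer's study. That study had 19 subjects, and the dose is above the 300 mg maximum here, so this is context and not evidence of harm at the trial doses.

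At stake is consistent application of a safety limit and, at reporting, whether a randomized subject with a low screening lymphocyte count belongs in the listing of eligibility failures planned in SAP section 9.3.

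**Working it through.** No calculation applies. The check compares the text across the two copies and within the sentence.

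**1. The five limits in 15a, as printed in both copies**

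| Analyte | Value | Comparison printed | Stands as an exclusion of its own |
|---|---|---|---|
| Hematocrit | 35% (men), 32% (women) | less than | yes |
| Neutrophils | 1500/uL | none | yes, but only as a single value |
| Lymphocytes | 900/uL | < | no, inside the exception bracket |
| Platelets | 120,000/uL | < | yes |
| INR | 1.4 | > | yes |

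Two of five limits are defective, and the defects are the same in section 8.3 and the synopsis.

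**2. Literal reading.** The neutrophil clause names a value and no direction, so it works only as an equality, which is no cutoff. The bracket opens with an exception and contains two items separated by a comma: a history of chronic benign neutropenia, and lymphocytes below 900/uL. No lymphocyte limit appears outside it. For illustration, a subject with neutrophils of 2500/uL and lymphocytes of 850/uL would not be excluded by 15a as printed.

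**3. Intended reading.** Item iii of the repeat list asks for a confirmatory lymphocyte count. That makes sense only if lymphocytes are an exclusion in their own right, so the list contradicts the bracket. An exception for benign neutropenia makes sense only if low neutrophils exclude, and the other blood-count limits in 15a all exclude low values. The intended limits are therefore neutrophils below 1500/uL unless chronic benign neutropenia is documented, lymphocytes below 900/uL, and platelets below 120,000/uL. The illustrative subject would then be excluded.

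**4. Could the '<' have been lost when the PDF was read?** It is unlikely, though the text alone cannot rule it out. Two other '<' signs survive in the same sentence, and the neutrophil sign is missing in both copies. Such a loss would also not move the lymphocyte limit inside a bracket.

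**5. What else would stop such a subject?**

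- The stem of criterion 15 is open-ended, so a clinically significant low count excludes whatever the bracket says.
- Section 9.2.1 excludes a result that stays abnormal on repeat.
- Exclusion 25 allows exclusion on judgement.
- The eligibility form puts the case before the medical monitor.

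The first three state no numeric neutrophil or lymphocyte limit. The form may do so, but it is not among the documents.

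**The case against.** The strongest reply is that this is a punctuation slip with little practical effect. Most investigators will read 15a as intended, and a subject with a low confirmed count meets several other barriers. That stands, and it is why the point is minor. It does not make the sentence correct, because the backstops rest on judgement or on an unspecified notion of abnormal, whereas 15a exists to give the number.

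A reader might infer more than the documents support, in five ways.

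- **INR is missing from the repeat list, so that is a further error.** The INR limit itself is printed correctly. The screening bullet that begins "Draw blood and prepare samples for coagulation testing (PT/INR), serum chemistry, hematology" names PT/INR and carries the general repeat rule, so a repeat is provided for. The four listed tests are all blood counts, so leaving INR out may be deliberate.
- **Lymphocytes are not measured.** Section 12.1.4 lists the leukocyte count together with "absolute counts of monocytes, neutrophils, basophils, eosinophils and platelets". The lymphocyte count follows as leukocytes minus the sum of neutrophils, monocytes, basophils and eosinophils.
- **The bar on waivers locks the misprint in.** Section 16.1.3 says "Protocol waivers will not be granted by the Sponsor in this study". Clarifying what a misprinted criterion means is not a waiver, and the eligibility form already brings each case to the medical monitor.
- **Subjects were wrongly enrolled.** The documents give no number of subjects affected, and the backstops make it impossible to infer one.
- **Analyses are affected.** SAP section 9.2 says major deviations may include failures of selected criteria, and nothing shows that 15a is among them. SAP section 9.3 is only a listing. Efficacy analyses use all randomized subjects.

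**Conclusion.** Exclusion 15a is wrong as written. The neutrophil limit lacks its '<', and the lymphocyte limit is inside an exception to which it does not belong, which contradicts item iii of the repeat list. This is a wording error in an operative entry limit, not a disputed design choice.

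The size is two of five limits in one sentence, in both copies. The practical effect is limited because other eligibility provisions partly cover the gap, and there is no effect on sample size or efficacy analyses. The conclusion assumes that the printed text is faithful to the signed protocol, which the surviving '<' signs and the duplicate copy support. It also assumes that the study manual does not already give sites the correct limits. If it does, the effect on sites is smaller still, but the protocol text still needs correcting.

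**What to change.** In section 8.3 and in the synopsis, replace the part of 15a from neutrophils onward, up to the repeat instruction, with:

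> absolute neutrophil count <1500/uL (except documented chronic benign neutropenia), absolute lymphocyte count <900/uL, or platelet count <120,000/uL; INR >1.4 or other coagulopathy

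The repeat list can stay as it is. The cost is one sentence in two places, with no new test, visit or threshold. Section 16.1.1 has an administrative class for typographical corrections and clarifications that do not bear on safety or science. Whether this one qualifies is for the sponsor to decide, since it touches a safety limit.

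If enrolment is already complete, which the documents do not state, the sponsor should record which reading of 15a was applied, so that the SAP 9.3 listing is compiled on one definition.
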